If the clinically significant laboratory, vital sign, or ECG abnormality is a sign associated with a confirmed disease or condition (e.g. elevated creatinine in a subject diagnosed with chronic kidney disease), only the diagnosis (chronic kidney disease) needs to be recorded on the AE eCRF (rather than listing individual test findings as AEs).

Separate instances of the same clinically significant laboratory, vital sign, or ECG abnormality across visits should not be recorded as separate AEs or SAEs.

7.1.4 *Deaths*

Any deaths that occur from the time of informed consent to the follow-up visit, regardless of attribution, must be reported within 24 hours of investigator's awareness of the death. See Safety Form Completion Instructions for complete instructions.

The Sponsor should be provided a copy of any post-mortem findings and/or relevant medical reports, including histopathology.

7.1.5 *Pregnancies and Contraception Requirements for Females*

For the purposes of this study, a female of childbearing potential is defined as any female who has experienced menarche and is pre-menopausal, unless permanently surgically sterile (e.g., hysterectomy, bilateral salpingectomy, bilateral oophorectomy). A postmenopausal state is defined as no menses for 12 months without an alternative medical cause in a previously menstruating female.

For the purposes of this study, acceptable contraception is defined below based on *Nonclinical Safety Studies for the Conduct of Human Clinical Trials and Marketing Authorization for Pharmaceuticals: ICH M3(R2)* dated January 2010, and other available guidelines ([“U.S. Medical Eligibility Criteria for Contraceptive Use” 2010](#); [“Recommendations related to contraception and pregnancy testing in clinical trials” 2014](#); [“M3\(R2\) Nonclinical Safety Studies for the Conduct of Human Clinical Trials and Marketing Authorization for Pharmaceuticals” 2010](#)):

All female subjects of childbearing potential must use highly effective contraception, which includes the use of one or more of the following acceptable methods:

1. Surgical sterilization (e.g., bilateral tubal occlusion or ligation, hysterectomy, bilateral salpingectomy, bilateral oophorectomy)
2. Total (as opposed to periodic or cyclic) abstinence from heterosexual intercourse, only if planned for the entire duration of the study period and consistent with the preferred and usual lifestyle for the subject
3. Hormonal contraception associated with consistent inhibition of ovulation; these may include (but are not necessarily limited to) oral, intravaginal, implantable, injectable, or transdermal delivery methods
4. Intrauterine device/system
5. Exclusive (sole) monogamous intercourse with a sterilized (i.e., vasectomized) or otherwise non-fertile (e.g., castrated) male partner; the male partner must have received medical assessment of the surgical success

Progesterone-only oral contraceptives are excluded as a highly effective method of contraception, as they do not consistently inhibit ovulation. Male or female condoms with or without spermicide, and female caps, diaphragms, and sponges with spermicide, or combinations (double barrier) are also excluded as highly effective contraceptive methods.

Any pregnancy occurring in a female subject or the female partner of a male subject, from the first study drug administration through the required follow-up visit must be reported within 24 hours of the investigator's awareness of the pregnancy. See Safety Form Completion Instructions for complete instructions.

The investigator will follow the pregnancy to delivery or other pregnancy outcome.

Pregnancy in a female clinical trial subject or female partner of a male clinical trial subject is not an SAE per se. Complications of such pregnancies (for example, spontaneous abortion) may qualify as SAEs and should be reported as such even if they occur after the Follow-up visit. Any congenital anomalies/birth defects must be recorded and reported as SAEs. See Safety Form Completion Instructions for complete instructions.

7.1.6 *Worsening of Pruritus or PN*

Pruritus or PN should be recorded as an AE or SAE only if considered by the investigator to have worsened in severity beyond the subject's typical fluctuations. It is important to include a description of the nature of the unexpected worsening when recording the AE or SAE (e.g. new PN lesions in previously uninvolved skin).

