- Important medical event (i.e. an event that may not result in death, be life-threatening, or require hospitalization, but which may be considered serious by the investigator or Sponsor, as it may jeopardize the subject and may require medical/surgical intervention to prevent one of the outcomes listed above). Examples of such medical events include allergic bronchospasm requiring intensive treatment in an emergency room or at home, blood dyscrasias or convulsions that do not result in inpatient hospitalization, or the development of drug dependency or drug abuse.

The following are not considered SAEs: a visit to the emergency room or other hospital department < 24 hours that does not result in admission (unless considered an important medical or life-threatening event), an elective surgery planned prior to signing consent, admission as per protocol for planned medical/surgical procedure, and/or routine health assessments requiring admission for baseline/trending of health status (e.g. routine colonoscopy).

The terms “severe” and “serious” are not synonymous. Severity refers to the intensity of an AE (e.g. mild, moderate, or severe pain); the event itself may be of minor medical significance (e.g. severe back pain). “Serious” is a regulatory definition, as defined above. Seriousness (not severity) serves as the basis for defining regulatory reporting obligations.

Severity and seriousness should be independently assessed when recording AEs and SAEs on the eCRF.

7.1.3 *Abnormal Physical Exam, Laboratory, Vital Sign, and Electrocardiogram Findings*

Abnormal physical exam findings that are clinically significant and are identified prior to the first dose of study drug should be recorded as medical history. New or worsening clinically significant abnormal physical exam findings identified after the first dose of study drug should be recorded as AEs.

Only abnormal laboratory, vital sign, and ECG findings that are considered clinically significant by the investigator (e.g. require active management or are associated with accompanying symptoms/signs) will be recorded as medical history or AEs on the eCRF. Abnormal laboratory, vital sign, and ECG findings that occur prior to the first dose of study drug should be recorded as medical history, and abnormal findings that occur after the first dose of study drug should be recorded as AEs.

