7 ASSESSMENT OF SAFETY

7.1 Definitions

7.1.1 *Adverse Event*

An AE is any untoward medical occurrence associated with the use of a drug in humans, whether or not considered drug related. An AE can be any unfavorable and unintended sign (e.g. an abnormal laboratory finding), symptom, or disease temporally associated with the use of a drug, without any judgment about causality.

AEs include treatment emergent exacerbations of pre-existing illnesses and AEs that occur as a result of protocol-mandated interventions.

7.1.2 *Serious Adverse Event*

An AE is considered “serious” if it results in any of the following outcomes:

- Death
- Life-threatening AE (i.e. the subject was at immediate risk of death from the event as it occurred. An event that might have led to death if it had occurred with greater severity is not “life-threatening”)
- Inpatient hospitalization or prolongation of existing hospitalization
- Persistent or significant incapacity or substantial disruption of the ability to conduct normal life functions
- Congenital anomaly/ birth defect
- Important medical event (i.e. an event that may not result in death, be life-threatening, or require hospitalization, but which may be considered serious by the investigator or Sponsor, as it may jeopardize the subject and may require medical/surgical intervention to prevent one of the outcomes listed above). Examples of such medical events include allergic bronchospasm requiring intensive treatment in an emergency room or at home, blood dyscrasias or convulsions that do not result in inpatient hospitalization, or the development of drug dependency or drug abuse.

The following are not considered SAEs: a visit to the emergency room or other hospital department < 24 hours that does not result in admission (unless considered an important medical or life-threatening event), an elective surgery planned prior to signing consent, admission as per protocol for planned medical/surgical procedure, and/or routine health assessments requiring admission for baseline/trending of health status (e.g. routine colonoscopy).

The terms “severe” and “serious” are not synonymous. Severity refers to the intensity of an AE (e.g. mild, moderate, or severe pain); the event itself may be of minor medical significance (e.g. severe back pain). “Serious” is a regulatory definition, as defined above. Seriousness (not severity) serves as the basis for defining regulatory reporting obligations.

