Severity and seriousness should be independently assessed when recording AEs and SAEs on the eCRF.

7.1.3 *Abnormal Physical Exam, Laboratory, Vital Sign, and Electrocardiogram Findings*

Abnormal physical exam findings that are clinically significant and are identified prior to the first dose of study drug should be recorded as medical history. New or worsening clinically significant abnormal physical exam findings identified after the first dose of study drug should be recorded as AEs.

Only abnormal laboratory, vital sign, and ECG findings that are considered clinically significant by the investigator (e.g. require active management or are associated with accompanying symptoms/signs) will be recorded as medical history or AEs on the eCRF. Abnormal laboratory, vital sign, and ECG findings that occur prior to the first dose of study drug should be recorded as medical history, and abnormal findings that occur after the first dose of study drug should be recorded as AEs.

If the clinically significant laboratory, vital sign, or ECG abnormality is a sign associated with a confirmed disease or condition (e.g. elevated creatinine in a subject diagnosed with chronic kidney disease), only the diagnosis (chronic kidney disease) needs to be recorded on the AE eCRF (rather than listing individual test findings as AEs).

Separate instances of the same clinically significant laboratory, vital sign, or ECG abnormality across visits should not be recorded as separate AEs or SAEs.

7.1.4 *Deaths*

Any deaths that occur from the time of informed consent to the follow-up visit, regardless of attribution, must be reported within 24 hours of investigator's awareness of the death. See Safety Form Completion Instructions for complete instructions.

The Sponsor should be provided a copy of any post-mortem findings and/or relevant medical reports, including histopathology.

7.1.5 *Pregnancies and Contraception Requirements for Females*

For the purposes of this study, a female of childbearing potential is defined as any female who has experienced menarche and is pre-menopausal, unless permanently surgically sterile (e.g., hysterectomy, bilateral salpingectomy, bilateral oophorectomy). A postmenopausal state is defined as no menses for 12 months without an alternative medical cause in a previously menstruating female.

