7.2.2 Eliciting Adverse Events

Investigators will seek information on AEs and SAEs at each subject contact through the follow-up visit. All AEs and SAEs, whether reported by the subject or noted by authorized study personnel, will be recorded in the subject's medical record and on the AE eCRF page, and, if serious, on the SAE form. For each AE and SAE recorded, the investigator will make an assessment of seriousness, severity, and causality.

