7.3 Follow-up of Adverse Events and Serious Adverse Events

The investigator must make every effort to follow all AEs and SAEs regardless of attribution until judged resolved or stabilized, the subject is lost to follow-up, or it has been determined that study drug treatment or participation in the study is not the cause of the AE or SAE.

7.4 Reporting Serious Adverse Events to the Sponsor and Institutional Review Board or Ethics Committee

The Sponsor or designee is under obligation to report certain SAEs to regulatory authorities related to investigational drugs in clinical trials. The Sponsor or designee must be notified within 24 hours of an AE when the investigator determines that an AE meets the protocol definition of an SAE, regardless of the cause or relationship to study drug.

An SAE related to study participation occurring before study drug administration and after informed consent should be promptly reported to the Sponsor. If the investigator learns of any SAE at any time after a participant has been discharged from the study, and the SAE is considered likely related to study drug, the SAE should be promptly reported to the Sponsor.

Please see the Safety Form Report Completion Instructions for safety reporting instructions.

The investigator must also comply with applicable requirements concerning reporting of SAEs to the IRB or Ethics Committee (EC). This may include initial or follow-up notification of an SAE or other safety information.

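### Protocol section 7.1.3 bars a separate AE or SAE record for a repeat laboratory, vital-sign or ECG abnormality, with no exception for recurrence or later seriousness, which conflicts with sections 7.2.2 and 7.4

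*Protocol*

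**What the plan says.** Protocol v4.0 section 7.1.3 sets the route by which test abnormalities become adverse events. The gate is clinical significance: "Only abnormal laboratory, vital sign, and ECG findings that are considered clinically significant by the investigator" are recorded. The section ends with the rule at issue: "Separate instances of the same clinically significant laboratory, vital sign, or ECG abnormality across visits should not be recorded as separate AEs or SAEs". It does not confine this to one continuing abnormality, it names SAEs, and it lists no exceptions.

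Three other parts of the protocol bear on the same event:

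- Section 7.2.2: "All AEs and SAEs, whether reported by the subject or noted by authorized study personnel, will be recorded", with serious ones also entered on the SAE form.
- Section 7.4: the sponsor must be notified "within 24 hours of an AE when the investigator determines that an AE meets the protocol definition of an SAE", whatever the cause. Repeat instances are not exempted.
- Section 7.2.3: when an AE changes in severity within a study period, the highest grade is kept. There is no matching instruction for a change in seriousness.

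SAP section 6.9.2 counts a subject once per system organ class and preferred term. The overview shell (Table 14.3.1.1.1) also has rows for the number of TEAEs and of serious TEAEs. Post-drug AEs are tabulated separately, overall and in weekly bins, by onset after the last dose (Tables 14.3.1.2.1.1 onward).

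**The concern.** A rule against duplicate records has a sound purpose: one raised transaminase seen at three visits should not become three AEs. The wording reaches further than that purpose. Separate instances naturally include an abnormality that went away and came back, and naming SAEs extends the bar to a later episode that is serious when the first was not.

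A site facing such an episode has one section telling it not to open a separate SAE and two others telling it to record and report all of them. Incidence of TEAEs and SAEs is a safety endpoint (protocol section 3.3.4). A recurrence, especially one after treatment stops, also carries information on causality that the first record does not hold.

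**Working it through.** No plan figure is at issue, so the check compares the texts and then traces one hypothetical subject through the SAP shells.

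**Texts side by side (protocol v4.0)**

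- 7.1.3: no separate AE or SAE for a separate instance; no exception.
- 7.2.2: all AEs and SAEs recorded; no exception.
- 7.4: 24-hour notification of any AE meeting the SAE definition; no exception.
- 7.2.3: highest grade kept. Section 7.1.2 treats severity and seriousness as different things to be assessed independently, so this does not carry a change to serious.

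For a second, serious episode of the same abnormality, 7.1.3 and 7.2.2 cannot both be followed literally. Sections 7.1.3 and 7.4 can both be met only by notifying the sponsor without a separate event record, or by upgrading the existing record, which no text instructs.

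**One hypothetical subject.** A clinically significant, non-serious ECG abnormality at Week 2 is normal at Weeks 4 and 10, then returns at Follow-up and is serious. All four are scheduled ECG visits (Appendix A, Table 2). The subject's contribution to each row is:

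| Row in the SAP shells | 7.1.3 as written, record not upgraded | 7.1.3 as written, record upgraded | Recurrence recorded as a new event |
|---|---|---|---|
| Subjects with any TEAE | 1 | 1 | 1 |
| Number of TEAEs | 1 | 1 | 2 |
| Subjects with a serious TEAE | 0 | 1 | 1 |
| Number of serious TEAEs | 0 | 1 | 1 |
| Subjects with a post-drug AE | 0 | 0 | 1 |
| Subjects with a serious post-drug AE | 0 | 0 | 1 |

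The first row does not change, because SAP 6.9.2 counts a subject once per term. The event count is short by one in both as-written columns. The post-drug rows stay at zero even with an upgrade, because the only record has its onset at Week 2.

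**Room for the pattern to arise.** With k scheduled post-dose assessments there are 2^k on/off patterns. One has no abnormality and k(k+1)/2 have a single unbroken run, so 2^k − 1 − k(k+1)/2 contain a gap and a return. Counting one Follow-up visit:

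- Endocrine tests (Week 10, Follow-up), k = 2: 4 − 1 − 3 = 0.
- Hematology and chemistry (Weeks 2, 10, Follow-up), k = 3: 8 − 1 − 6 = 1.
- ECG (Weeks 2, 4, 10, Follow-up), k = 4: 16 − 1 − 10 = 5.
- Vital signs (Weeks 2, 4, 6, 10, Follow-up), k = 5: 32 − 1 − 15 = 16.

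These are possible patterns, not probabilities. Unscheduled tests add to them. The documents give no recurrence rate, so an expected number of lost events cannot be computed.

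**The case against.** The strongest reply is that the rule is narrow and the rest of the plan covers the gap. It bars only a separate record. The first instance is still recorded, followed until resolved or stabilized (section 7.3), and kept at its highest grade. Section 7.4 stays in force, and nothing forbids changing an existing record to serious. An abnormality belonging to a confirmed disease is recorded as the diagnosis. Subject incidence is counted once per term, and laboratory summaries, shift tables and listings do not depend on AE recording (SAP section 6.9.3). Scheduled blood draws leave little room for resolution and return. The safety form instructions that the protocol cites, which are not available here, may settle the convention.

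Most of this stands and limits the size. Three parts do not close the gap. Keeping the highest grade concerns severity, not seriousness. The laboratory listing shows values, ranges and clinical significance, but not AE seriousness or causality. Upgrading a record is sensible but not instructed, and it does not restore a recurrence to the post-drug tables.

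A reader might infer that the rule allows serious events to go unreported. The documents do not support that: section 7.4 has no exemption for repeats, so this is a contradiction to reconcile, not a permission.

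**Conclusion.** The conflict is real and is in the current text. Its effects are limited to three outputs: counts of TEAEs and serious TEAEs, which can be too low; the post-drug AE tables, which lose a recurrence whose first instance began on treatment; and the number of subjects with a serious TEAE, which is too low only if the first instance was non-serious and its record is not upgraded. Subject-level TEAE incidence by preferred term is unaffected, provided the first instance was recorded as an AE under the same term. The size cannot be estimated from the documents. The efficacy analyses are not touched.

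A reader might also infer that stable pre-existing abnormalities will be counted as treatment-emergent. The physical-exam rule asks for change ("New or worsening clinically significant abnormal physical exam findings identified after the first dose of study drug should be recorded as AEs"), while the rule for tests says only that "abnormal findings that occur after the first dose of study drug should be recorded as AEs". The documents do not support that inference. The same section says "Abnormal laboratory, vital sign, and ECG findings that occur prior to the first dose of study drug should be recorded as medical history"; section 7.1.1 says "AEs include treatment emergent exacerbations of pre-existing illnesses", which requires a change; and the SAP shells define TEAEs by onset after the first dose. An unchanged finding from screening, measured again at Week 2, has no such onset. Nor is there a basis for claiming lost power to detect a drug effect on AEs: the AE shells carry no hypothesis test, and the documents give no background prevalence for such findings.

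**What to change.** In section 7.1.3, replace the closing sentence with text to this effect:

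- Repeated measurements of one continuing abnormality are one AE; an abnormality that returns after resolution is recorded as a new AE or SAE.
- An abnormality that becomes serious is captured as serious and reported under section 7.4.

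For the second item, choose either upgrading the existing record or opening a new one, and use it throughout. Both are defensible. Opening a new record for an event that never resolved splits it in two and raises the event count, so the choice should be stated in the eCRF completion guide.

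The cost is about two sentences, a matching line in that guide, and a few more event records. No visits or tests are added. Adding a condition of new or worse to the laboratory, vital-sign and ECG rule, to match the physical-exam rule, is optional harmonization of wording.

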7.2 Methods and Timing for Recording and Reporting Adverse Events

7.2.1 *Adverse Event Reporting Period*

Any AE occurrence during the study must be recorded on source documentation and eCRF at the site, in accordance with protocol instructions.

AEs and SAEs will be recorded from the first study drug administration through the follow-up visit. After the required follow-up visit, only SAEs that are believed to be drug-related should be reported.

After informed consent, but prior to initiation of study drug, only SAEs considered by the investigator to be caused by a protocol-mandated intervention will be collected (e.g. SAEs related to invasive procedures such as blood collection). These procedure-related SAEs should only be reported on the source documents and SAE form, not on the AE eCRF. Subjects who undergo screening procedures but are not randomized into the study will not have SAEs recorded in the clinical database.

7.2.2 *Eliciting Adverse Events*

Investigators will seek information on AEs and SAEs at each subject contact through the follow-up visit. All AEs and SAEs, whether reported by the subject or noted by authorized study personnel, will be recorded in the subject's medical record and on the AE eCRF page, and, if serious, on the SAE form. For each AE and SAE recorded, the investigator will make an assessment of seriousness, severity, and causality.

7.2.3 *Assessment of Severity*

All AEs entered into the eCRF will be graded for severity using the National Cancer Institute Common Terminology Criteria for Adverse Events (NCI CTCAE) v4.03 ([“Common Terminology Criteria for Adverse Events \(CTCAE\)” 2010](#)) to describe the maximum intensity of the adverse event.

If the AE cannot be found in the event-specific NCI CTCAE grading criteria, the investigator should use the definitions for Grade 1, 2, 3, and 4 in [Table 1](#).

Table 1 Adverse Event Grading

Grade	Severity	Alternate Description ^a
1	Mild (apply event-specific NCI CTCAE grading criteria)	Asymptomatic or mild symptoms; clinical or diagnostic observations only; intervention not indicated.
2	Moderate (apply event-specific NCI CTCAE grading criteria)	Minimal, local or noninvasive intervention indicated; limiting age-appropriate instrumental activities of daily living (ADL ^b)
3	Severe (apply event-specific NCI CTCAE grading criteria)	Severe or medically significant but not immediately life-threatening; hospitalization or prolongation of hospitalization indicated; disabling; limiting self care ADL ^c
4	Very severe, life threatening, or disabling (apply event-specific NCI CTCAE grading criteria)	Life-threatening consequences; urgent intervention indicated.
5	Death related to AE	

^a Use these alternative definitions for Grade 1, 2, 3, and 4 events when the observed or reported AE is not in the NCI CTCAE listing. A semi-colon indicates 'or' within the alternate description of the grade.

^b Instrumental ADL refer to preparing meals, shopping for groceries or clothes, using the telephone, managing money, etc.

^c Self care ADL refer to bathing, dressing and undressing, feeding self, using the toilet, taking medications, and not bedridden.

Source: National Cancer Institute Common Terminology Criteria for Adverse Events (NCI CTCAE) v4.03

Note that severity, a measure of intensity, is not equivalent to seriousness, a regulatory definition of outcome. Regardless of severity, some AEs may meet the criteria for seriousness. See [Section 7.1.2](#) for the definition of an SAE.

If an adverse event changes in severity during the same study period (e.g., treatment period), only the highest severity grade will be recorded on the eCRF.

